5.6.4 Selection of Doses in the Study

Risankizumab is currently in Phase 3 development for treatment of subjects with moderate to severe chronic plaque psoriasis. Four Phase 3 studies are currently ongoing, planning to enroll approximately 2100 subjects, and evaluating risankizumab dose of 150 mg administered at Week 0, 4 and thereafter E12W. Subjects from these ongoing Phase 3 studies will enter in the current study. Hence, the 150 mg dose administered E12W is selected for this study, so the subjects will continue to receive the same dose as in preceding Phase 3 studies to establish the long-term safety and efficacy of risankizumab. In Japanese Phase 2/3 Protocol 1311.38 some subjects (N = 56) will be treated with risankizumab 75 mg E12W dose. As risankizumab has been well tolerated in the completed and ongoing studies, and based on preliminary PK results indicating no clinically meaningful difference in exposure between Japanese and Caucasian subjects, (approximately 30% higher exposure in Japanese subjects compared to Caucasian subjects) AbbVie considers it appropriate to investigate 150 mg E12W dosing paradigm in these Japanese subjects.

Subjects currently enrolled in BI clinical Trial 1311.13 will also be offered the opportunity to continue receiving treatment for chronic plaque psoriasis with risankizumab in Study M15-997. One-hundred and ten subjects were enrolled in this trial and were treated with risankizumab 90 mg SC E12W with the option to increase the dose to 180 mg if there was evidence of lack of response.

Preliminary results from the pivotal Phase 3 studies support the clinical benefit of the 150 mg dose of risankizumab in subjects with moderate to severe plaque psoriasis. Approximately 1300 subjects received treatment with risankizumab 150 mg SC and all four pivotal trials achieved their co-primary endpoints which were defined as achievement

of $\geq 90\%$ reduction from baseline PASI score (PASI 90) at Week 16 and achievement of a sPGA score of clear or almost clear at Week 16.

Subjects treated with risankizumab experienced substantial skin clearance and clinical improvement in the extent and severity of plaque. Across the four pivotal studies, the proportion of subjects with PASI 90, sPGA score of clear or almost clear, and PASI 100 at Week 16 ranged from 72 – 75%, 84 – 88%, and 36 – 51%, respectively.

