9.0 Study Drug Exposure and Compliance

Study drug exposure (days) will be summarized using the sample size, mean, standard deviation, minimum, median and maximum. Study drug exposure will be summarized as follows:

Risankizumab Exposure (in Days):

The Risankizumab Exposure (total duration during the preceding study and Study M15-997) will be defined as follows:

The Risankizumab Exposure = Last risankizumab dose date – First risankizumab dose date (either in Study M15-997 or preceding study) + 84 days, except:

- The Risankizumab Exposure in the Retreatment Population is defined as: Last risankizumab dose date – First retreatment of risankizumab date (either in Study M15-997 or preceding study) + 84 days
- The Risankizumab Exposure in the ALL_RZB Population among subjects who were re-randomized to placebo during Study 1311.4 Part B is defined as: Last risankizumab dose date during Study 1311.4 Part A – First risankizumab dose date + 84 days + Last risankizumab dose date – First retreatment of risankizumab date + 84 days

In addition, number of subjects who have at least one dose of self-injected study drug during Study M15-997 will also be summarized.

A data cutoff date (September 01, 2017) was applied during the first interim analysis in 2017.

A data cutoff date (November 01, 2021) will be applied during the second interim analysis. The duration of study drug exposure will be defined up to this cutoff date.

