11.0 Safety Analysis

11.1 General Considerations

Safety analyses will include adverse events, laboratory, local tolerability, and vital sign measurements.

For the safety analyses, a baseline value (BL_RZB) is defined as the last non-missing observation on or prior to the date of the first dose of Risankizumab either in Study M15-997 or the preceding studies whichever is the earlier.

For subjects from Japan among the RZB, RZB_NL, Retreatment and UST_RZB Populations, only data prior to the start of risankizumab 75 mg dose will be used in the safety analyses. This subgroup analysis will only be performed in the final analysis, upon study completion.

When summarizing the safety for risankizumab 150 mg among the ALL_RZB Population, safety data collected (i) from feeder studies not using risankizumab 150 mg dose and/or (ii) from subjects in Japan who have started the risankizumab 75 mg dose will not be included for the safety summary of risankizumab 150 mg dose.

For the RZB Japan Population, safety data will be summarized regardless of dose.

Summaries of treatment-emergent adverse events (TEAEs), potentially clinically important laboratory values and vital sign values, and liver function tests will be provided for all populations. Analysis of change from baseline in laboratory values and vital sign values, shift tables and local tolerability will be provided for RZB, RZB_NL, UST_RZB, ADA_RZB, FUM_RZB, RZB Japan populations.

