11.2 Analysis of Adverse Events

11.2.1 Treatment-Emergent Adverse Events

Treatment emergent adverse events (TEAEs) are defined as any event with an onset date that is after the first dose of risankizumab and with an onset date within 140 days after the last dose of study drug in the analysis period except:

- **TEAE of Retreatment:** TEAE are defined as any event with an onset date that is after the first dose of retreatment and no more than 140 days after the last dose of study drug, and prior to the start of risankizumab 75 mg (if any, for subjects in Japan).
- **TEAE of ALL_RZB (any dose):** TEAEs are defined as any event with an onset date after the first dose of risankizumab through 140 days after the last dose of risankizumab, except for AEs with an onset date during protocol-designed treatment gaps (i.e., placebo period in subjects re-randomized to placebo during Study 1311.4 Part B) that was more than 140 days from the last dose of previous risankizumab treatment and before the first dose of retreatment in the ALL_RZB Population.
- **TEAE of RZB, RZB_NL, UST_RZB, ADA_RZB, FUM_RZB and ALL_RZB (150 mg):** TEAEs are defined as any event with an onset date after the first dose of risankizumab 150 mg through 140 days after the last dose of risankizumab 150 mg, and prior to the start of risankizumab 75 mg (if any, for subjects in Japan), except for AEs with an onset date during protocol-designed treatment gaps (i.e., placebo period in subjects re-randomized to placebo during Study 1311.4 Part B) that was more than 140 days from the last dose of

previous risankizumab 150 mg treatment and before the first dose of retreatment in the ALL_RZB Population.

Events where the onset date is the same as the study drug start date are assumed to be treatment emergent, unless the adverse event start time is prior to the study drug start time. If an incomplete onset date is collected for an adverse event, the event will be assumed to be treatment-emergent unless there is other evidence that confirms that the event is not treatment-emergent (e.g., the event end date is prior to the study drug start date).

The number and percent of subjects experiencing treatment-emergent TEAEs will be tabulated using the Medical Dictionary for Drug Regulatory Activities (MedDRA[®]) system organ class and preferred term.

Summary tables will be presented as follows:

1. Adverse Event Overview

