Serious Infections	Serious AEs in the Infections and Infestations SOC	
Active Tuberculosis	Active Tuberculosis CMQ (code 80000188)	
Opportunistic Infections excluding tuberculosis and herpes zoster	Opportunistic infection excluding tuberculosis and herpes zoster CMQ (code 80000189)	
Injection Site Reactions	Narrow	Injection site reaction CMQ (code 80000019)
Malignancies	Narrow	Malignant tumours (SMQ 20000194)
Non-melanoma Skin Cancer (NMSC)	Broad	Skin malignant tumours (SMQ 20000204) excluding terms identified by the Melanoma CMQ (code 80000119)
Malignant Tumours excluding NMSC	'Malignant Tumours excluding NMSC' is identified by the 'Malignant Tumours' search excluding terms identified by the 'Non-melanoma skin cancer (NMSC)' search.	
Hypersensitivity	Narrow	Hypersensitivity (SMQ 20000214)
Serious hypersensitivity reactions	Narrow	Serious AEs in the Hypersensitivity (SMQ 20000214)
Adjudicated Anaphylactic Reaction*	Adjudicated terms will be identified using SDTM data (e.g., CE and PR domains).	
Hepatic Events	Broad	Hepatic failure, fibrosis and cirrhosis and other liver damage-related conditions (SMQ 20000013)
	Broad	Hepatitis, non-infectious (SMQ 20000010)
	Broad	Cholestasis and jaundice of hepatic origin (SMQ 20000009)
	Broad	Liver related investigations, signs and symptoms (SMQ 20000008)
	Narrow	Liver-related coagulation and bleeding disturbances (SMQ 20000015)

* Events will be identified for adjudication by Anaphylactic Reaction SMQ Broad search as specified in the RISA AAC Charter.

Adverse Event per 100 Patient-Years of Exposure

Adverse events occurring during the analysis period for each population will be presented by event rate per 100 patient-years. These will be presented for any TEAEs, serious adverse events, Areas of Special Interest.

AEs per 100 patient-years of exposure is defined as the number of AEs divided by the total exposure in 100 patient-years. Note that one event per preferred term per day per subject will be counted in the calculation of the number of AEs (i.e., a preferred term will not be counted twice on the same day for the same subject). See the calculation method below.

$$100 \times \frac{\text{Number of TEAEs}}{\text{Total Patient Years}}$$

where total patient years is defined as the sum of the study drug exposure (defined as date of last dose – date of first dose + 140 days (5 half-lives)) of all subjects normalized by 365.25, and rounded to one decimal place.

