11.6 Safety Subgroup Analysis

For RZB, RZB_NL, Retreatment and UST_RZB Populations, AE overview tables will be provided in the subgroup including subjects from Japan only. This subgroup analysis will only be performed in the final analysis, upon study completion.

In addition, the number and percentage, as well as exposure adjusted event rate of hypersensitivity events and injection site reactions will also be summarized among the ALL_RZB Population (150 mg), by the anti-drug antibody (ADA) status during the analysis period.

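### The patient-years behind the 150 mg event rates can run past the Japanese 75 mg start, where 150 mg events stop counting; the bias is downward and small once pooled

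*SAP*

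**What the plan says.** **Denominator.** Rates per 100 patient-years are planned for each population. SAP 11.2.1 takes total patient-years as the "sum of the study drug exposure (defined as date of last dose – date of first dose + 140 days", summed over all subjects and divided by 365.25. It does not say which dose counts as first or last, and it does not stop at a change to 75 mg.

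**Numerator.** In the same section, events for the 150 mg summaries count from the first 150 mg dose over a window that includes a 140-day tail, with its end worded as "after the last dose of risankizumab 150 mg, and prior to the start of risankizumab 75 mg (if any, for subjects in Japan". The Retreatment rule also stops at the 75 mg start. The populations concerned are RZB, RZB_NL, Retreatment, UST_RZB and ALL_RZB (150 mg). The same event rule names ADA_RZB and FUM_RZB, but SAP 5.1 sets no Japanese 75 mg restriction for them.

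**General data rules.** For Japanese subjects in RZB, RZB_NL, Retreatment and UST_RZB, SAP 11.1 says that "only data prior to the start of risankizumab 75 mg dose will be used in the safety analyses". For ALL_RZB (150 mg), data "from subjects in Japan who have started the risankizumab 75 mg dose will not be included for the safety summary". Neither sentence mentions patient-years or the 140-day tail.

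**Where the rate is used.** Besides the rates for each population, SAP 11.6 plans that the "exposure adjusted event rate of hypersensitivity events and injection site reactions will also be summarized among the ALL_RZB Population (150 mg"), by anti-drug antibody status.

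**Doses before the extension.** Protocol 5.6.4 states: "In Japanese Phase 2/3 Protocol 1311.38 some subjects (N = 56) will be treated with risankizumab 75 mg E12W dose". All subjects then receive 150 mg at the extension Baseline visit (Protocol 5.1).

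**The concern.** An exposure-adjusted rate needs events and person-time from the same interval. Here the event count closes at the 75 mg start and the person-time formula does not. Time in which no event can count enters the denominator and can only lower the rate. Long-term safety is the primary objective, and these rates are one of its main summaries. Two programmers following the text could also arrive at different denominators.

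The event rule has a related wording problem. It assumes that 75 mg always follows 150 mg. For subjects from the 75 mg arm of Study 1311.38 the order is reversed, so a literal cut at the 75 mg start comes before their first 150 mg dose and removes every 150 mg event they have in the extension.

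**Working it through.** The plan states no event rate or patient-year total, so there is no figure to reproduce. One constant can be checked: 20 weeks × 7 = 140 days.

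**Inputs.** Dosing every 12 weeks = 84 days (Protocol 5.1). Tail = 140 days (SAP 11.2.1). Last target day 2129, Week 304 (SAP Table 1). Planned enrolment about 2200 (SAP 4.3). Assumed, because the documents do not say: 1% to 10% of subjects switch, at Week *w* = 100, 148 or 208 after their first 150 mg dose.

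**Method.** The event count is the same whichever denominator is used, so stated rate ÷ matched rate = matched days ÷ stated days. For a switcher, matched days = 7*w*. For a completer who never switches, both are (2129 − 1) + 140 = 2268 days.

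**75 mg dose records removed.** The last 150 mg dose falls 84 days before the switch, so stated days = 7*w* − 84 + 140 = 7*w* + 56. The excess is 140 − 84 = 56 days.

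**Formula applied to all doses.** Stated days = 2268, because dosing continues at 75 mg.

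| Switch | Matched days | Shortfall, 75 mg records removed | Shortfall, all doses |
|---|---|---|---|
| Week 100 | 700 | 1 − 700/756 = 7.4% | 1 − 700/2268 = 69% |
| Week 148 | 1036 | 1 − 1036/1092 = 5.1% | 1 − 1036/2268 = 54% |
| Week 208 | 1456 | 1 − 1456/1512 = 3.7% | 1 − 1456/2268 = 36% |

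An earlier switch does more: with the last 150 mg dose at Week 48, the ratio is 420/476 = 0.882, a 12% shortfall. If 75 mg began at the 14-day minimum gap (Protocol 5.5.4), the excess would be 140 − 14 = 126 days.

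**Pooled, 75 mg records removed.** Shortfall = 56*p* ÷ [(1 − *p*) × 2268 + *p* × (7*w* + 56)].
- *p* = 1%, Week 100: 0.56 ÷ (2245.32 + 7.56) = 0.02%.
- *p* = 10%, Week 100: 5.6 ÷ (2041.2 + 75.6) = 0.26%.
- A rate of 3.0 becomes 2.99 at most. The table shells show one decimal.

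**Pooled, all doses.** Shortfall = *p* × (1 − 7*w*/2268).
- *p* = 1%, Week 208: 0.4%.
- *p* = 10%, Week 100: 6.9%, so 3.0 becomes 2.79.

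**Cross-check on other assumptions.** Take 2200 subjects, 50 to 200 switchers, the last 150 mg dose at Week 96 to 204, and all others dosed to Week 252. With 75 mg records removed, the pooled ratio is 0.9972 to 0.9993 (8 to 31 excess patient-years). With all doses it is 0.945 to 0.995 (54 to 629 excess patient-years).

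**Subjects from the 75 mg arm of 1311.38.** They fall outside RZB and RZB_NL, which are limited to 150 mg, so the affected summary is ALL_RZB (150 mg). Extension time per completer is 252 × 7 + 140 = 1904 days = 5.21 patient-years. For 56 subjects this is 292 patient-years with no countable event. Against 2200 × 1904 ÷ 365.25 = 11,468 extension patient-years it is about 2.5%. This is an upper figure: it assumes that all 56 enrol and complete, and that their time stays in the denominator.

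**The case against.** The strongest reply is that SAP 5.1 and 11.1 already confine these analyses to data before the 75 mg start, and that SAP 11.2.1 ties the rates to each population's analysis period. If person-time is part of the data so confined, it ends where the events end and there is no mismatch. That is a sensible intention, but the SAP does not state it. The mention of the analysis period qualifies the adverse events, while the denominator has its own explicit formula with a fixed 140-day tail. Where the authors wanted exceptions to exposure they wrote them: SAP 9.0 starts from "The Risankizumab Exposure = Last risankizumab dose date – First risankizumab dose date (either in Study M15-997 or preceding study) + 84 days" and then sets separate rules for Retreatment and for the placebo gap in Study 1311.4.

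Much of the rest of the reply stands. A reader might go further in three ways that the documents do not support:

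- **That all later 75 mg time is in the denominator.** This gives the 36% to 69% figures, but it needs 75 mg dose records to enter analyses that SAP 5.1 and 11.1 restrict to earlier data. It shows what the unqualified formula permits, not the likely result.
- **That 90 mg or 180 mg time from Study 1311.13 inflates the 150 mg denominator.** Of that study Protocol 5.6.4 says "One-hundred and ten subjects were enrolled in this trial and were treated with risankizumab 90 mg SC E12W". SAP 11.1 keeps safety data from feeder studies that did not use 150 mg out of the 150 mg summary.
- **That Japan-only rates would be visibly distorted.** SAP 11.6 plans only adverse event overview tables for that subgroup, and SAP 11.2.1 defines the overview by numbers and percentages of subjects. The RZB Japan Population and ALL_RZB (any dose) are summarized regardless of dose and do not have this mismatch.

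**Conclusion.** The mismatch is in the text of SAP 11.2.1. For a subject whose 75 mg starts less than 140 days after the last 150 mg dose, the stated denominator exceeds the time in which a 150 mg event can count, so the rate is biased low. With 75 mg records removed and dosing on schedule, the size is about 4% to 7% per switcher for a switch at Week 208 to Week 100, and under 0.3% in a pooled rate if 1% to 10% switch. The pooled effect would not normally show at one decimal. It reaches several percent only if the formula is applied literally to all doses. These sizes rest on assumed switching, since neither the number nor the timing is given.

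The literal loss of extension 150 mg events for up to 56 subjects from the 75 mg arm of 1311.38 is a separate wording fault in the event rule and in SAP 11.1. If their person-time were dropped as well, the rate would not be diluted, but their 150 mg experience would still be missing from the ALL_RZB (150 mg) summary.

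This is of minor priority: the direction is certain for such switchers, the likely pooled size is small, and the correction is cheap.

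**What to change.** In SAP 11.2.1, define each population's patient-years as the time inside that population's own treatment-emergent window. For the 150 mg summaries:

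- Start at the first 150 mg dose, or at the first retreatment dose for Retreatment.
- End at the earliest of the last 150 mg dose + 140 days, the day before the first 75 mg dose given after a 150 mg dose, and the data cut-off.
- For ALL_RZB subjects re-randomized to placebo in Study 1311.4 Part B, sum two segments, in keeping with the two-segment rule of SAP 9.0. Exclude gap time that is more than 140 days after the last Part A dose and before retreatment. A single continuous interval would retain placebo time in which the event rule counts nothing.

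Use the phrase *first 75 mg dose given after a 150 mg dose* in SAP 11.1 and in the event rule as well, so that subjects from the 75 mg arm of 1311.38 keep their extension 150 mg events.

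As a wording clarification only, SAP 10.1 could state that the 75 mg start ends the period for last-observation-carried-forward. Its reasoning about carrying values forward under the same treatment already points that way.

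The cost is a few sentences in the SAP and matching programming. Dose dates are already recorded (Protocol 5.5.5), no new data or protocol change is needed, and the SAP is to be signed off before database lock (SAP 3.0).

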8.1.5 Safety Analysis

All AEs, SAEs, AEs leading to discontinuation, and pre-specified AESIs will be collected during the study. A treatment-emergent AE (TEAE) is defined as an event with onset or worsening after the first study dose of a risankizumab (either in a preceding Phase 2/3 psoriasis study or this study) and within 20 weeks (140 days) after the last study drug injection. The number and percentages of subjects experiencing TEAE will be tabulated using the Medical Dictionary for Drug Regulatory Activities (MedDRA[®]) system organ class and preferred term. Summaries (including percentages and event per 100 patient-years) of SAEs, deaths, AEs leading to discontinuation from the study, and pre-specified AESIs will be provided as well. Mean change in laboratory and vital signs variables will be summarized. For selected parameters, a listing of all subjects with clinically significant laboratory or vital sign values will be provided. Shift tables for changes from baseline according to the normal range will also be provided.

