Program Source Code: /[name]/SDA/ABBV-066/Psoriasis/CSR/M15-997/G/14.3/PCMS_RUN/s1311_31_aesi.sas

Table 14.3__2
Subjects with Treatment-Emergent AESI
(RZB Population)

Category MEDDRA 20.0 Preferred Term	RZB (N=) n (%)
<hr/>	
Subjects with:	
Fungal Infections	
...	XXX (XX.X)
...	XXX (XX.X)
Herpes Zoster	XXX (XX.X)
...	XXX (XX.X)

Program Source Code: /[name]/SDA/ABBV-066/Psoriasis/CSR/M15-997/G/14.3/PCMS_RUN/s1311_31_aesi.sas

Table 14.3__3
 Subjects with Treatment-Emergent Hypersensitivity by Subgroup
 (RZB Population)

Subgroup	RZB
Status	(N=)
Category	n (%)
MEDDRA 20.0 Preferred Term	
<hr/>	
Antidrug Antibody Positive Status (Yes, No)	
Yes	
Hypersensitivity	XXX (XX.X)
xxx	XXX (XX.X)
...	XXX (XX.X)
Anaphylactic Reaction	XXX (XX.X)
...	XXX (XX.X)
No	
Hypersensitivity	XXX (XX.X)
xxx	XXX (XX.X)

Program Source Code: /[name]/SDA/ABV-066/Psoriasis/CSR/M15-997/G/14.3/PCMS_RUN/s1311_31_aesi.sas

Table 14.3_4
 Subjects with Treatment-Emergent Injection Site Reaction by Subgroup
 (RZB Population)

Subgroup	RZB
Status	(N=)
MEDDRA 20.0 Preferred Term	n (%)
Antidrug Antibody Positive Status (Yes, No)	
Yes	XXX (XX.X)
xxx	XXX (XX.X)
No	XXX (XX.X)
xxx	XXX (XX.X)

Program Source Code: /[name]/SDA/ABV-066/Psoriasis/CSR/M15-997/G/14.3/PCMS_RUN/s1311_31_aesi.sas

Table 14.3__5
 Treatment-Emergent Adjudicated CV Adverse Events
 (RZB Population)

Category Sub-Category	RZB (N=) (PYS=) Events (E/100PY)
Subjects with:	
MACE	
Myocardial Infarction	XXX (XX.X)
...	XXX (XX.X)
Extended MACE	XXX (XX.X)
Myocardial Infarction	XXX (XX.X)
...	XXX (XX.X)
Other CV Events	XXX (XX.X)

Program Source Code: /[name]/SDA/ABBV-066/Psoriasis/CSR/M15-997/G/14.3/PCMS_RUN/s1311_31_aesipy.sas

Table 14.3__6
 Treatment-Emergent AESI
 (RZB Population)

Category MEDDRA 20.0 Preferred Term	RZB (N=) (PYS=) Events (E/100PY)
Subjects with:	
Fungal Infections	XXX (XX.X)
...	XXX (XX.X)
...	XXX (XX.X)
Herpes Zoster	XXX (XX.X)
...	XXX (XX.X)

Program Source Code: /[name]/SDA/ABBV-066/Psoriasis/CSR/M15-997/G/14.3/PCMS_RUN/s1311_31_aesipy.sas

Table 14.3__7
 Treatment-Emergent Hypersensitivity by Subgroup
 (RZB Population)

Subgroup	RZB
Status	(N=)
Category	(PYS=)
MEDDRA 20.0 Preferred Term	Events (E/100PY)
Antidrug Antibody Positive Status (Yes, No)	
Yes	
Hypersensitivity	XXX (XX.X)
Dermatitis	XXX (XX.X)
...	XXX (XX.X)
Anaphylactic Reaction	XXX (XX.X)
...	XXX (XX.X)

Program Source Code: /[name]/SDA/ABV-066/Psoriasis/CSR/M15-997/G/14.3/PCMS_RUN/s1311_31_aesipy.sas

Table 14.3__8

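### As written, the SAP 11.2.1 patient-year formula counts 1311.4 Part B placebo-gap time in which ALL_RZB events are excluded, so the error can only lower ALL_RZB rates or leave them unchanged

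*SAP*

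**What the plan says.** **Denominator.** SAP 11.2.1 presents event rates for each population. It divides the number of TEAEs by total patient-years, summed from "study drug exposure (defined as date of last dose – date of first dose + 140 days (5 half-lives)) of all subjects". No population or treatment gap is excepted.

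**Numerator.** The TEAE definitions in the same section carve out part of the placebo period for ALL_RZB subjects re-randomised to placebo in 1311.4 Part B. For any dose, an event is dropped if its onset falls in a placebo period "that was more than 140 days from the last dose of previous risankizumab treatment and before the first dose of retreatment". The 150 mg definition repeats the exclusion for events more than 140 days after "previous risankizumab 150 mg treatment and before the first dose of retreatment in the ALL_RZB Population".

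**Exposure summary.** SAP 9.0 has a separate rule for the same subjects in ALL_RZB: "Last risankizumab dose date during Study 1311.4 Part A – First risankizumab dose date + 84 days + Last risankizumab dose date", minus the first retreatment date, plus a further 84 days. For the second interim analysis it adds: "The duration of study drug exposure will be defined up to this cutoff date".

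**Membership.** SAP 5.1 places everyone dosed in M15-997 in ALL_RZB, so re-randomised 1311.4 subjects who rolled over are included.

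**The concern.** A rate per 100 patient-years needs its events and its time to come from the same window. Here they do not: time between day 140 after the last Part A dose and the first retreatment dose is counted as exposure, but events in it are excluded.

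Long-term safety is the primary objective, and Protocol 8.1.5 plans rates per 100 patient-years for SAEs, deaths, discontinuations due to AEs and AESIs. SAP 11.6 also plans exposure-adjusted hypersensitivity and injection-site reaction rates by ADA status in ALL_RZB (150 mg). For a safety summary, an error that can act only toward lower rates is the less acceptable direction. Numbers and percentages of subjects, listings, and any population without re-randomised 1311.4 subjects are not touched. No hypothesis test is planned.

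**Working it through.** The SAP states no patient-year total or rate, so there is no planned figure to reproduce. The check is person-time algebra for one re-randomised subject.

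**Notation.** A = days from first to last Part A dose; G = days from last Part A dose to first retreatment dose; B = days from first retreatment dose to last dose.

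- As written (SAP 11.2.1): A + G + B + 140.
- Matched to the ALL_RZB TEAE windows: A + min(G, 140) + B + 140.
- Excess: max(0, G − 140) days, in which no counted event can lie.
- SAP 9.0 rule: A + 84 + B + 84.

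**Example** (assumed A = 112, B = 1764 days):

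| G (days) | As written | Matched | Excess | Excess / as written | SAP 9.0 |
|---|---|---|---|---|---|
| 140 | 2156 | 2156 | 0 | 0% | 2044 |
| 200 | 2216 | 2156 | 60 | 2.7% | 2044 |
| 400 | 2416 | 2156 | 260 | 10.8% | 2044 |
| 600 | 2616 | 2156 | 460 | 17.6% | 2044 |

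Substituting SAP 9.0 would not cure the mismatch. Once G is at least 140, it falls 2 × (140 − 84) = 112 days short of the event windows per gap subject, which makes rates too high.

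**Do such gaps exist?** The exclusion clause has a purpose only if some gaps exceed 140 days. SAP Tables 6 and 7 also give windows for subjects whose retreatment began only at OLE entry.

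**Effect on the whole ALL_RZB rate.** Excess PY = n × (G − 140)/365.25; fall in rate = excess/(correct PY + excess). The number of gap subjects n, the gap G and the correct PY are all assumptions. For scale, 2200 subjects × (252 × 7 + 140) days / 365.25 = 11,468 PY if everyone completes the OLE. Feeder-study time would add to this and dropout would reduce it.

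| n | G | Correct PY | Excess PY | Fall in rate |
|---|---|---|---|---|
| 50 | 168 d (24 wk) | 12,000 | 3.83 | 0.03% |
| 100 | 196 d (28 wk) | 11,000 | 15.3 | 0.14% |
| 200 | 280 d (40 wk) | 11,000 | 76.7 | 0.69% |
| 200 | 364 d (52 wk) | 11,000 | 122.7 | 1.10% |
| 300 | 616 d (88 wk) | 11,000 | 391.0 | 3.43% |
| 300 | 616 d (88 wk) | 7,500 | 391.0 | 4.95% |

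The last two rows need every assumed subject to have an 88-week gap. That is unlikely, because SAP Table 5 covers subjects retreated after relapse, on a schedule separate from those first retreated in the OLE.

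**Would it show in print?** The Appendix A rate shells use one decimal. In the 52-week row a fall of at least 0.1 needs a rate of at least 0.1/0.0110 = 9.1 per 100 PY. A rate of 200.0 would print as 200 × (1 − 0.01103) = 197.8; a rate of 0.3 becomes 0.297 and still prints as 0.3.

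**The case against.** The strongest reply is that the SAP already shows the gap should come out. Section 9.0 splits exposure for exactly these subjects, and Section 11.2.1 ties the rates to each population's analysis period. A programmer reading both might well split the time, leaving only a missing cross-reference. That is good evidence of intent, but Section 11.2.1 carries its own formula in parentheses, and the split in Section 9.0 has the wrong tails for the event windows. Neither text gives the right denominator. What does stand is that the downward direction belongs to the literal reading; the Section 9.0 split would err upward.

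The size is also open to challenge. It rests on assumptions, the 88-week and 7,500 PY cases trace to nothing in the documents, and with no comparator arm and no test a shift of about 1% changes no decision. This is fair, and those cases should be read as outer bounds only.

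The visible rate shells are for the RZB population, which does not draw on 1311.4, so they show the print format and not an affected table. The effect on rates by ADA status cannot be sized: a small stratum rich in gap subjects could move more than the overall rate, but nothing in the documents shows that one exists.

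**Conclusion.** The concern holds. The formula in SAP 11.2.1 conflicts with the ALL_RZB event windows in the same section and adds max(0, G − 140) event-free days per affected subject. Under the literal reading this mechanism can only lower the ALL_RZB rates, for any dose and for 150 mg, or leave them unchanged. The overall effect is probably small: about 1% in the assumed central case of 200 subjects, 52-week gaps and 11,000 PY. Mainly the high any-TEAE rates would change visibly; rare-event rates would usually print the same. It should still be fixed, because the rule is wrong as written for a planned summary under the primary objective and is cheap to correct.

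**What to change.** In SAP 11.2.1, for subjects re-randomised to placebo in 1311.4 Part B, define ALL_RZB patient-years (any dose and 150 mg) in days, before dividing by 365.25, as:

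[min(last Part A dose + 140 days, first retreatment date) − first dose] + [last dose + 140 days − first retreatment date]

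State that the 84-day exposure in Section 9.0 serves the exposure summary only.

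Two related clarifications can go in at the same time:

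- **Interim analyses.** Cap the final segment at the data cutoff, in line with the cutoff sentence in Section 9.0. With dosing every 12 weeks, an ongoing subject on schedule is 0 to 84 days past the last dose at cutoff, so an uncapped 140-day tail credits 56 to 140 unobserved days (0.15 to 0.38 PY).
- **First and last dose.** State that they follow each population's TEAE window: from the first retreatment dose for Retreatment, and from first to last 150 mg dose for the 150 mg summaries, stopping at any switch to 75 mg in Japan. This is a clarification, not a demonstrated bias.

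The cost is a few lines of SAP text and one extra derivation from dates already collected. The gap correction removes no counted event; relative to the literal formula, ALL_RZB rates rise slightly or stay the same.
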